	
To assess whether early preventive radiation of the high-risk asymptomatic or minimally symptomatic bone metastases in patients with metastatic cancer can decrease the number of symptomatic skeletal related events (SSEs) by measuring the time to an SSE in any bone metastasis or death due to any cause.
 
SSEs are defined as:
 
 - symptomatic pathological fracture - spinal cord compression leading to neurological deficit or pain - Indication for palliative radiotherapy (for bone pain, cord compression or (impending) fracture) - Indication for orthopedic surgery (for bone pain, cord compression or (impending) fracture) 
Secondary objective and endpoint:
 
 • To evaluate the need for hospitalization by comparing the number of hospitalizations related to the high-risk bone metastase(s) between systemic therapy/observation (arm A / observational arm) and upfront RT (arm B / upfront RT arm) from time of study randomization to date of death of any cause or last follow-up visit (24m after randomization date) or early end of participation in the study due to other reasons. • To assess overall survival from time of study randomization to date of death of any cause or last follow-up visit (24m after randomization date) • To evaluate quality of life using the EORTC QLQ-C15-PAL questionnaire (see appendix 2) and the EuroQol Group EQ-5D-5L questionnaire (see appendix 3) • To evaluate acute (if related to RT for patients in arm B \leq 90 days after the last RT dose) and late (if related to RT for patients in arm B $>$ 90 days after the last RT dose) toxicity by assessing adverse events in both study arms from the time of ICF signing to last follow-up visit (24m after randomization date), death of any cause or early end of participation in the study due to other reasons using the National Cancer Institute Common Terminology Criteria for Adverse Events (NCI-CTCAE) v5.0 (see appendix 4). Only adverse events that are related to the bone metastatic disease or related to the radiotherapy (only for patients in arm B) will be reported in the eCRF.
Study duration:	48 months

Schedule of events

Table 1 Assessments during screening, treatment and follow upⁱ

	Screening	Enrollment	Treatment period ^{a,h,i}		Follow-up period ^{h,i}	

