5.2 Allocation to treatment groups and blinding

This is a randomized controlled trial. Due to the type of intervention, blinding is not possible.

Randomization will be completed on a per patient basis (not lesion based) in a 1:1 ratio to the observational arm receiving systemic therapy / observation (Arm A) or to the arm receiving early RT plus systemic therapy / observation (Arm B). Randomization will be performed by the site staff in the window between screening and start of treatment using an electronic randomization tool in the eCRF that uses variable block randomization as randomization algorithm.

The following stratification factors are taken into consideration for randomization:

- NRF prognostic class (0-1 vs 2)
- high-risk disease location (spine location vs. other)
- bone modifying agents (yes vs. no).

Assignment of the subject identification number

At screening, each potential study participant will be assigned a subject identification number that will be retained as the primary identifier for the subject throughout their participation in the study. The subject-id consists of a sequential 6-digit number (comprised of a 2-digit study site number -11, 12, etc.- and a 4-digit number incremental per center representing the sequential order in which they are screened: 110001, 110002, etc.), so that each subject is numbered uniquely across the entire database. Upon signing the ICF, the subject is assigned to the next sequential subject-id available to the Investigator through the electronic data capture system.

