8.1.4 Causal relationship of an AE/SAE to the intervention

The Investigator is obligated, and will use clinical judgement, to assess the relationship between study treatment and each occurrence of each AE/SAE. Furthermore, the investigator will assess the relationship between the bone metastatic disease and each occurrence of each AE/SAE. Only AE/SAE that are related to the bone metastatic disease or related to radiotherapy (only applicable for patients in arm B) will be reported using the National Cancer Institute Common Terminology Criteria for Adverse Events (NCI-CTCAE) v5.0 (see appendix 4). The relationship of each AE/SAE to the study intervention should be characterized using one of the following: related to RT, related to bone metastatic disease or unrelated.

Table 3 Adverse event causal relationship with study treatment

Related to RT (only applicable for patients in arm B)	There is a reasonable possibility that the RT is the cause of the AE.
Related to bone metastatic disease	There is a reasonable possibility that the bone metastatic disease is the cause of the AE.
Unrelated	There is no reasonable possibility that the RT or the bone metastatic disease is the cause of the AE.

8.1.5 Expectedness of an SAE:

The following definitions are general guidelines to help assign grade of attribution:

Adverse reaction (AR): any AE caused by a study treatment.

Suspected adverse reaction (SAR): any AE for which there is a reasonable possibility that the study treatment caused the AE.

Unexpected: an event is considered unexpected if its nature or severity is not consistent with a recognized side-effect of the study treatment.

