8.2 Reporting procedures

8.2.1 Method of detecting (S)AE

AE will be reported by the subject. Care will be taken not to introduce bias when detecting AE and/or SAE. Open-ended and non-leading verbal questioning of the subject is the preferred method to inquire about AE occurrences. For each SAE, it should be evaluated whether it concerns an SSE. If it concerns an SSE, the SAE should be documented as such in the eCRF and the necessary actions should be taken (see section 6.2). In case hospitalization occurs, it should be evaluated whether the hospitalization is related to the high-risk bone metastasis(es) and this information should be documented in the eCRF.

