9.3 Statistical methods for analysing primary and secondary outcomes

Primary objective:

The primary endpoint (SSE-free survival) is a composite endpoint of SSEs and death (death before SSE is part of the endpoint, not a competing risk). The primary endpoint is time until the occurrence of SSE in any bone metastasis or death from the date of randomization whichever occurs first. Data suggest that the median SSE-free survival is around 10.4 months. With a HR of 0.5, we hypothesize that the median SSE-free survival will be 20.8 months.

A proportion of patients will have multiple high-risk bone lesions. Pain will be reported lesion-based, however the SSE-free survival remains patient-based as this is more clinically relevant.

Secondary objectives

- The number of **hospitalizations** related to the high-risk metastase(s) will be compared between systemic therapy / observation (arm A) and upfront RT plus systemic therapy / observation (arm B) from date of study randomization to last follow-up visit (24m after randomization date), date of death of any cause or early end of participation in the study due to other reasons
- **Overall survival** will be assessed from time of study randomization to date of death of any cause or last follow-up visit (24m after randomization date)
- **Quality of life** will be compared between systemic therapy / observation (arm A) and upfront RT plus systemic therapy / observation (arm B), using the EORTC QLQ-C15-PAL questionnaire (see appendix 2) and the EuroQol Group EQ-5D-5L questionnaire (see appendix 3)
- **Adverse events** in both study arms will be evaluated using the National Cancer Institute Common Terminology Criteria for Adverse Events (NCI-CTCAE) v5.0 (see appendix 4) from the time of ICF signing to last follow-up visit (24m after randomization date), date of death of any cause or early end of participation in the study due to other reasons. Only adverse events that are related to the bone metastatic disease or related to the radiotherapy (only for patients in arm B) will be reported in the eCRF.

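### Adverse events reach the eCRF through an attribution filter that differs by arm, so the two-arm toxicity data cannot give an unbiased contrast for radiotherapy-type events

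*Protocol*

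**What the plan says.** The synopsis sets a secondary objective of evaluating acute and late "toxicity by assessing adverse events in both study arms". Section 2 (Table 2) and section 9.3 repeat the two-arm scope. Section 9.3 then limits what is entered: "Only adverse events that are related to the bone metastatic disease or related to the radiotherapy (only for patients in arm B". The same limit stands in the synopsis, footnote j of the schedule of events, section 2, section 8.1.4 and section 8.2.2.

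Section 8.1.4 has the investigator classify each event by clinical judgement as "related to RT, related to bone metastatic disease or unrelated". The first label in its table reads "Related to RT (only applicable for patients in arm B". The bar for using it is low: "There is a reasonable possibility that the RT is the cause of the AE". An event is unrelated, and so stays out of the eCRF, when "There is no reasonable possibility that the RT or the bone metastatic disease is the cause of the AE". Systemic therapy has no category of its own, although patients in either arm may receive it (section 5.1).

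Section 5.2 states: "Due to the type of intervention, blinding is not possible". On overlap with the primary endpoint, section 8.2.1 says of a serious event: "If it concerns an SSE, the SAE should be documented as such in the eCRF".

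Two places are worded without the filter. Section 6.1.2 asks for any toxicity in the treatment period to be entered in the database. Section 8.2.3 asks for every serious adverse event to go to the sponsor within 24 hours.

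**The concern.** A randomised control arm is useful for safety because it shows how often nausea, fatigue or diarrhoea occur without the intervention. That requires both arms to be recorded by the same rule. Here an event is recorded only after a causality judgement by someone who knows the arm, and one of the two qualifying judgements is available in arm B only. Arm A therefore supplies no attribution-free background rate, and a later analysis plan cannot recover events that were never entered.

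The filter can also lose information in arm B. A true RT effect that the investigator puts down to concurrent systemic therapy is coded unrelated and not entered.

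At stake is a secondary safety endpoint in a phase III trial meant to establish preventive RT in patients with few or no symptoms. The primary endpoint is not affected.

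**Working it through.** The protocol gives no adverse event rate or attribution rate, so there is no stated figure to reproduce. The check has three parts.

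**1. Which events are recorded (sections 8.1.4, 8.2.2, 9.3)**

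| Investigator's judgement | Arm A | Arm B |
|---|---|---|
| Bone disease is a possible cause | recorded | recorded |
| RT is a possible cause | code not available | recorded |
| Systemic therapy or another cause only | not recorded | not recorded |

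The arms differ in the second row only, and an unblinded judgement controls that row.

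**2. Illustration of size, assuming RT causes no events**

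Let b be the true proportion of patients with a background event, equal in both arms. Let s be the share judged possibly due to bone disease, equal in both arms. Let a be the share of the remainder that arm B investigators call possibly RT-related.

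- Recorded in arm A: b × s
- Recorded in arm B: b × [s + (1 − s) × a]
- False excess in arm B: b × (1 − s) × a

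b, s and a are assumptions. The 60 patients per arm come from section 9.1.

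| b | a | s | Arm A | Arm B | Excess (points) |
|---|---|---|---|---|---|
| 10% | 25% | 0 | 0% | 2.5% | 2.5 |
| 20% | 50% | 0 | 0% (0 of 60) | 10% (6 of 60) | 10 |
| 40% | 75% | 0 | 0% (0 of 60) | 30% (18 of 60) | 30 |
| 20% | 50% | 10% | 2% | 0.20 × (0.10 + 0.90 × 0.50) = 11% | 9 |
| 40% | 50% | 10% | 4% | 0.40 × (0.10 + 0.90 × 0.50) = 22% | 18 |

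With s = 0 the excess runs from 0.10 × 0.25 = 2.5 points to 0.40 × 0.75 = 30 points. Letting 10% of background events enter both arms as bone-related multiplies the excess by 0.9. It shrinks but does not disappear. If events are recorded regardless of attribution, both arms record b and the expected difference is 0.

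**3. Consistency of the rule**

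Sections 8.1.4, 8.2.2 and 9.3 filter by attribution. Section 6.1.2 (treatment period) and section 8.2.3 (serious events to the sponsor) do not. A site following 6.1.2 would enter a systemic-therapy event from the first weeks that a site following 8.2.2 would leave out.

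**The case against.** The strongest reply is that the protocol plans no between-arm test of adverse events. Hospitalisations and quality of life are to be compared; adverse events are only to be evaluated. Acute and late toxicity are defined by days since the last RT dose, for RT-related events in arm B. The endpoint can thus be read as a description of RT toxicity, and Amendment 2 adopted the filter deliberately to spare sites from recording irrelevant symptoms. This stands as far as it goes: describing RT-attributed events in arm B is legitimate. It does not explain why the objective covers both arms, and the workload rationale does not address the asymmetry.

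Four stronger readings are tempting, and the documents do not support them.

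- *Arm A must show zero RT-type events.* The bone-disease code uses the same reasonable-possibility bar in both arms, so fatigue or loss of appetite can enter arm A that way.
- *The trial is likely to report a significant false excess.* With b = 20%, a = 50% and s = 0, a Fisher test at 60 per arm would be nominally significant in 56% of trials. But no such test is stated, and the figure runs from 0.4% to about 100% over the assumed range. It is 7% at b = 20%, a = 25% and s = 10%.
- *The trial cannot compare harm at all.* QLQ-C15-PAL asks both arms about pain, nausea, appetite, weakness, tiredness and constipation with no attribution step, and section 9.3 plans to compare it. It does not cover vomiting, diarrhoea, dysphagia or skin reactions, and under section 6.2 it stops after a symptomatic skeletal event (SSE).
- *Fewer SSEs in arm B will hide RT toxicity in a total count.* Nothing says that the two kinds of event will be pooled; they carry separate codes. Two of the four SSE types are indications for treatment, which need not appear as adverse events.

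**Conclusion.** The point holds in a limited form. The recording rule differs by arm and depends on unblinded attribution, so the recorded data cannot support an unbiased between-arm statement on RT-type events. The illustrated false excess of about 2.5 to 30 percentage points rests wholly on assumed background (10-40%) and attribution (25-75%) rates, with no RT effect and no background event judged bone-related. It shows direction and possible scale and is not a forecast. The conflict between sections 6.1.2 and 8.2.3 on one side and 8.1.4, 8.2.2 and 9.3 on the other is on the page and needs no assumption. This is a worthwhile, inexpensive improvement to a secondary safety endpoint, and it has to be made while data are still being collected.

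**What to change.** 1. In sections 8.1.4, 8.2.2 and 9.3, add a short fixed list of CTCAE v5.0 terms, recorded at each scheduled visit in both arms regardless of attribution. Candidates are fatigue, nausea, vomiting, diarrhoea, dysphagia or oesophagitis, dermatitis and pain flare. Keep attribution as a separate field, and keep the Amendment 2 filter for all other terms.
2. Base any between-arm toxicity statement on that list and on the QLQ-C15-PAL symptom scores. Say that the questionnaires stop after an SSE and that, as section 6.2 stands, the list would stop too. The 1- and 3-month visits should be least affected.
3. Present RT-attributed events as a description of arm B only, and tabulate bone-disease and SSE-flagged events separately.
4. Reconcile sections 6.1.2 and 8.2.3 with the filter, stating which events go to the eCRF and which only to the sponsor.

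The cost is a protocol amendment and a handful of tick-box items on a form for visits where adverse events are already assessed. That gives back a little of the workload Amendment 2 saved. Items 2 and 3 need analysis and reporting wording only. The list removes the attribution step, but it does not remove the reporting bias that any open trial carries.

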5.1 Description

Patients will be randomized (1:1) to receive either systemic therapy/observation (Arm A) or early RT plus systemic therapy / observation (Arm B).

Arm A:

The observational arm (Arm A) will include **observation or systemic therapy**, according to the treating physician's discretion. Systemic therapy may include continuation of the current systemic therapy or initiation of a new systemic therapy.

These patients will be able to receive palliative RT to progressed, painful lesions (an SSE) only at the time of symptom worsening (NRS > 2/10 or need for opioids) or determination of spinal cord compression with neurological symptoms or (high risk for) fracture requiring surgical intervention. Upfront preventive RT is not allowed.

Arm B:

The intervention in this study is **early, upfront radiation therapy** to asymptomatic or minimally symptomatic (defined as high-risk) bone metastases. Up to 5 high-risk asymptomatic or minimally symptomatic metastatic locations per patient are allowed.

The radiotherapy (RT) doses used will be in accordance with common practice palliative RT schedules. As such a single fraction of 8 Gy is considered for all patients, except for patients with a very good prognosis (NRF prognostic score 0-1) in which a higher dose will be used with SABR [Chow et al].

Table 3: Predictive model for estimation of median overall survival (OS): NRF-model [Chow et al].

Three variables:

- **Primary cancer type** -> risk factor: non breast/prostate/lung cancer
- **Site of metastases** -> risk factor: metastases other than bone
- **Karnofsky performance score (KPS)** -> risk factor: KPS ≤60

0-1 risk factors	median OS 64 weeks	95%CI: 37-undefined
2 risk factors	median OS 28 weeks	95% CI 22-34
3 risk factors	median OS 10 weeks	95% CI 8-13

Simulation:

All patients will be immobilized in a comfortable and stable position to irradiate the metastatic lesion(s). Support and/or immobilization devices will be used to increase patient comfort or to ensure set-up reproducibility. A planning CT scan will be acquired without intravenous contrast with <3mm CT slice thickness (1mm for SABR) encompassing the region of interest with sufficient margin for treatment planning, a typical scan length should extend at least 10 cm superior and inferior beyond the treatment field borders. The isocenter will be placed in the middle of the affected bone lesion.

Target volume definition:

1. *Conventional radiotherapy:*

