8.2.2 Period for collecting AE and SAE information

During the period from main ICF signing to the last follow-up visit (24m after randomization date), date of death of any cause or early end of participation in the study due to other reasons, all (S)AE that are related to the bone metastatic disease or related to radiotherapy (only applicable for patients in arm B) will be documented in both study arms.

The following applies for (S)AE related to RT (arm B):

Toxicity that appears within 90 days after the last RT dose will be regarded as acute toxicity.

Toxicity that appears >90 days after the last RT dose administration will be regarded as late toxicity.

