8.2.3 Investigator reporting of an (S)AE to the sponsor

When an AE/ SAE occurs, it is the responsibility of the Investigator to review all documentation (e.g., hospital progress notes, laboratory reports, and diagnostics reports) related to the event.

The Investigator will then record all relevant AE/ SAE information in the eCRF. Each event must be recorded separately.

There may be instances when copies of medical records for certain cases are requested by. In this case, all subject identifiers, with the exception of the subject number, will be redacted on the copies of the medical records before submission.

The Investigator will attempt to establish a diagnosis of the event based on signs, symptoms, and/or other clinical information. Whenever possible, the diagnosis (not the individual signs/symptoms) will be documented as the AE/ SAE.

The investigator shall report all serious adverse events immediately (<24h), after first knowledge, to the sponsor. Information regarding SAE will be transmitted to the sponsor using the SAE form, which must be completed and signed by a physician from the study site and transmitted to the sponsor ([contact]) within 24 hours. The investigator will submit any updated SAE data to the Sponsor within 24 hours of it being available.

All SAE that have not resolved by the end of the study or that have not resolved upon discontinuation of the subject's participation in the study, must be followed until any of the following occurs:

- the event resolves
- the event stabilizes
- the event returns to baseline, if a baseline value/status is available
- the event can be attributed to agents other than the treatment or to factors unrelated to study conduct
- it becomes unlikely that any additional information can be obtained (subject or health care practitioner refusal to provide additional information, lost to follow-up after demonstration of due diligence with follow-up efforts)

The immediate and follow-up SAE reports shall identify subjects by patient specific study numbers.

The following situations do not need to be reported as SAE:

- Elective hospitalization for pre-existing conditions that have not been exacerbated by the treatment;
- A hospitalization which was planned before the patient consented for study participation and where admission did not take longer than anticipated;
- Social and/or convenience admission to a hospital;

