10.1.4 Benefit-risk assessment

This study will be performed in accordance with ethical principles that have their origin in the Declaration of Helsinki and are consistent with ICH, GCP, and applicable regulatory guidelines.

To further minimize any potential risk, careful monitoring of each subject will be conducted throughout the study to detect any adverse events (AE) or safety signals, as delineated in the schedule of events.

Potential risks of study participation

The intervention in this study is early, upfront radiation therapy to asymptomatic or minimally symptomatic bone metastases.

In general, a single fraction of 8 Gy will be prescribed according to general recommendations for patients with painful bone metastases. This single day treatment is characterized by its **limited patient burden**. Radiation dose and planning will follow international guidelines and will be delivered with contemporary radiation techniques, thereby **minimizing the side effects for** patients [Oldenburger et al, Nguyen et al, Lutz et al].

Potential benefits of study participation

The aim of this trial is reducing the number of SSEs, inherently a **symptom-based endpoint**. Therefore, the hypothesis of the project is to decrease symptoms and side effects for each individual patient.

Risk-benefit assessment

According to the ESTRO-ACROP recommendations, the majority of patients experience no or mild acute toxicity after conventional radiotherapy, the possibility of experiencing side effects should not be a reason to withhold patients with bone metastases from this treatment. No high-grade side effects are expected.

Patients in the observational arm will not receive RT but have the possibility to receive palliative RT to progressed, painful lesions (an SSE) only at the time of symptom worsening.

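### RT-related adverse events can be recorded only in arm B, although arm A patients may receive palliative RT, so any side-by-side toxicity table sets arm B against a structural zero

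*Protocol*

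**What the plan says.** **Endpoint.** Table 2 and section 9.3 make acute and late toxicity a secondary endpoint. Adverse events are evaluated in both arms from consent to 24 months, death or early end of participation.

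**Recording rule.** Section 9.3 limits the eCRF to events related to the bone metastatic disease or "related to the radiotherapy (only for patients in arm B) will be reported in the eCRF". The synopsis, Table 2 and footnote j of Table 1 say the same. Section 8.1.4 states: "Only AE/SAE that are related to the bone metastatic disease or related to radiotherapy (only applicable for patients in arm B) will be reported". Section 8.2.2 has events "related to radiotherapy (only applicable for patients in arm B) will be documented in both study arms", so one sentence both restricts by arm and refers to both arms.

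**Causality table (8.1.4).** The first category is headed "Related to RT (only applicable for patients in arm B", in brackets. The second is relation to the bone metastatic disease. The third, *Unrelated*, applies only when neither RT nor the bone disease is a reasonably possible cause.

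**RT in arm A.** Section 5.1 says of arm A: "These patients will be able to receive palliative RT to progressed, painful lesions (an SSE) only at the time of symptom worsening", and adds cord compression with neurological symptoms and fracture risk as further triggers. Section 10.1.4 repeats it: "Patients in the observational arm will not receive RT but have the possibility to receive palliative RT". An indication for palliative RT is itself one of the four SSE components.

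**After an SSE.** Footnote h of Table 1 and section 6.2 call for one set of visit assessments, preferably within a week. From then on only survival and further SSEs are recorded.

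**SAE reporting.** Section 8.2.3 says, without an arm restriction: "The investigator shall report all serious adverse events immediately (<24h", to the sponsor.

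**The concern.** The trial contrasts RT given early with RT given, if at all, once an SSE occurs. Some arm A patients will therefore be irradiated as part of the strategy they were randomised to. If toxicity from RT can be labelled as such in one arm only, the toxicity tables do not measure the same thing in the two columns. This is a data-collection rule: an analysis plan cannot recover events that were never entered, or were entered under the wrong cause.

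At stake is the benefit-risk reading of upfront RT. The distortion tends to run against the experimental arm, and it touches a secondary safety endpoint, not the primary analysis.

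**Working it through.** **Step 1. Where can an arm A event go?** Take a non-serious toxicity in an arm A patient that is due only to palliative RT given at an SSE.

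- *Related to RT*: closed to arm A.
- *Unrelated*: not permitted, because RT is a reasonably possible cause.
- *Related to bone metastatic disease*: open, but a misattribution.

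No category is correct, and the reporting rule gives no route into the eCRF as an RT event. The recorded count of RT-related events in arm A is zero whatever the true rate.

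**Step 2. Reproduce the planning figures (section 9.1).** Inputs: HR 0.5, alpha 0.05 (taken as two-sided), power 0.80, 2-year SSE-free survival of 20% in arm A.

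- Events: 4 x (1.960 + 0.842)^2 / (ln 0.5)^2 = 65.3; the protocol states 65.
- Arm B survival at HR 0.5: 0.20^0.5 = 0.447, so the event probabilities are 0.80 (A) and 0.553 (B), mean 0.676.
- Patients: 65 / 0.676 = 96.1 (stated 96); 96 / 0.8 = 120 (stated 120).
- Split of events with 48 per arm: 48 x 0.80 + 48 x 0.553 = 38.4 + 26.5 = 64.9.

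**Step 3. Arm A patients who might be irradiated.** First events in arm A by 24 months, deaths included, are 38.4 on 48 evaluable patients, or 60 x 0.80 = 48 if all 60 randomised are followed. The protocol gives no share of first events that lead to RT. Assume 30-50%:

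| Base | 30% | 50% |
|---|---|---|
| 38.4 events | 11.5 | 19.2 |
| 48 events | 14.4 | 24.0 |

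That is about 12 to 24 patients, or 24-40% of arm A (0.80 x 0.30 to 0.80 x 0.50). Looser assumptions widen this. If 25-75% of first events are SSEs and 30-90% of those lead to RT, the share runs from 0.80 x 0.25 x 0.30 = 6% to 0.80 x 0.75 x 0.90 = 54%, about 4 to 32 of 60.

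**Step 4. Effect on a side-by-side table (illustration).** Let t be the toxicity rate per RT course, assumed equal in both arms; uA and uB are the shares of each arm irradiated at an SSE. Counting per course, the true difference is t x (1 + uB - uA). Take t = 20% (assumption) and the same 30-50% in arm B, so uB = 0.553 x 0.30 to 0.553 x 0.50 = 17-28%.

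- If AEs are collected to 24 months as 8.2.2 says, the recorded difference is t x (1 + uB). The overstatement is t x uA: 4.8 points (uA = 24%) to 8.0 points (uA = 40%).
- If recording stops at the SSE as footnote h and 6.2 say, arm B loses its post-SSE RT toxicity too and the recorded difference is t. The overstatement falls to t x (uA - uB): 20 x (0.240 - 0.166) = 1.5 points to 20 x (0.400 - 0.277) = 2.5 points. Late toxicity of the upfront course arising after an SSE would also be lost, which narrows it further by an amount that cannot be derived.

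**Step 5. Is lifting the arm restriction enough?** No. Arm A RT follows an SSE, and that is when footnote h and 6.2 end AE recording. Apart from the one set of assessments around the SSE, most arm A RT toxicity, including all late toxicity, would still be missed.

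**The case against.** The strongest defence is that the restriction is deliberate. Amendment 2 brought it in with a stated reason, to avoid listing irrelevant symptoms. Section 8.1.4 concerns causality to the intervention, and the intervention is upfront RT. On that view the endpoint describes the toxicity of the study treatment, and palliative RT in arm A is outside it. This explains the rule but does not rescue it. Toxicity of the modality under study is hardly irrelevant, the endpoint is said to cover both arms, and the causality table leaves arm A RT events without a valid category.

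Three further objections stand and limit the point.

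- A reader might infer that the protocol plans a formal between-arm toxicity test that will be biased. It does not: hospitalisations and quality of life are to be compared, whereas adverse events are to be evaluated. The problem applies to any side-by-side table or benefit-risk statement built on these data.
- A reader might infer that RT harms in arm A go entirely unseen. Section 8.2.3 sends all serious events to the sponsor, and events with a possible bone-disease cause are reportable in arm A. What is lost is the RT label in the eCRF and non-serious toxicity due only to RT.
- The number affected is not in the protocol. The endpoint counts an indication for RT, not RT given, and includes deaths. Equal toxicity per course is also doubtful, since section 5.1 plans SABR for arm B patients with NRF score 0-1.

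**Conclusion.** The point holds as a recording asymmetry. Under the protocol as written, RT-related toxicity in arm A is a structural zero, and tables that place the arms side by side will tend to overstate the excess toxicity of upfront RT. That finding rests on the text alone.

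The size is unknown. About 12 to 24 arm A patients is a reasonable illustration, resting on the assumed 30-50% share and on 38 to 48 first events. The effect in percentage points rests further on an assumed toxicity rate, and on which of two contradictory rules sites follow after an SSE. The post-SSE stop is a partial offset, because it also removes arm B toxicity, so no large net bias can be claimed. Confidence is high on the mechanism and low on the magnitude. The change should be made; the primary endpoint is unaffected.

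**What to change.** 1. Remove the arm B restriction in the synopsis, Table 2, footnote j of Table 1, section 8.1.4 and its causality table, section 8.2.2 and section 9.3. Section 6.1.1 repeats the wording, but no study RT has been given at screening, so a change there only serves consistency.
2. Record adverse events related to any bone radiotherapy given during the study, in both arms and with the same causality categories. Capture the dates of each course (footnote h and 6.2 ask for location and reason only) and apply the 90-day acute/late split per course.
3. Tabulate toxicity of upfront RT and of SSE-triggered RT separately. This keeps the description of the study intervention that the present rule aims at.
4. Amend footnote h and section 6.2 so that RT-related AE collection continues after an SSE, in both arms, to the end of the window in 8.2.2. Without this, step 1 achieves little.
5. Reconcile 8.2.3, which covers all SAEs, with 8.1.4 and 8.2.2, which cover only some.

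**Cost:** a protocol amendment, a small eCRF change, and extra AE entry for patients who have had an SSE, at follow-up visits already planned for survival and further SSEs. Events not recorded before the change may be hard to recover, so it should come early.
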